### 14.13 Publication Policy

This section details the collaboration contractual terms relating to the data ownership and publication policy for Diurnal Ltd and the participating investigators stemming from the data generated from this study.

The study results will be published irrespective of the study outcome. The sponsor and Principal Coordinating Investigator will jointly arrange for the preparation of one or more manuscripts. The sponsor's and investigator's comments on the proposed publication(s) shall be considered in good faith by the authors. Publication of the results will not include company confidential information without the permission of the sponsor.

The sponsor may announce summary data in order to comply with Financial and other Regulatory Authorities, whilst ensuring that release of such data will not compromise the investigator's liability to publish the data in appropriate scientific forms. Announcements made prior to the first scientific publication of the data will be reviewed by the Principal Coordinating Investigator.

Data from individual study sites (unless the only site of a study, or a circumscribed sub-study) will not be published separately unless exceptional circumstances prevail.

#### **14.14 Clinical Study Report**

The results of the study will be presented in an integrated clinical study report according to GCP and ICH-E3 guidance.

#### **14.15 Data Retention and Availability**

The investigator is required to maintain all study documentation, including regulatory documents, copies of eCRFs, signed ICFs, and records for the receipt and disposition of study medications, for a period of two years following approval date of a New Drug Application for the drug, or until 15 years after completion of the study, whichever is later.

During the study, the investigator must make study data accessible to the sponsor, ethics committee/IRB and regulators including the FDA. A file for each subject must be maintained that includes the signed ICF and copies of all source documentation related to that subject. The investigator must ensure the availability of source documents from which the information on the eCRF was derived.

#### **14.16 Study Termination**

The study may be terminated prior to completion of the specified number of subjects at the request of the sponsor, the investigator, the ethics committee/IRB or Regulatory Authority or by mutual agreement. Conditions that may warrant early termination include, but are not limited to, insufficient adherence to the protocol requirement, the discovery of a significant, unexpected and unacceptable risk to the subjects, attainment of study objectives, or at the discretion of the sponsor. Procedures for terminating the study will be agreed upon by both the sponsor and the investigator.

## Appendix 1 - Sampling Schedule for 24-hour Profiling

Sample Number	Clock time in hours
1	15:00
2	17:00
3	19:00
4	21:00
5	23:00
6	01:00
7	03:00
8	05:00
9	07:00
10	09:00
11	11:00
12	13:00
13	15:00

Endocrine profile: Beginning at 15:00h on Day 1 (Visit 1.1) and finishing 15:00h on Day 2 (Visit 1.2): two hourly serum for:

- 17-OHP
- A4

Exact times of samples to be recorded; allowable deviation from above times is  $\pm 10$  minutes

The above will be repeated on respective Days for Visits 2 (2.1 and 2.1), 3 (3.1 and 3.2) and 4 (4.1 and 4.2).

If dosing with the study medication needs to be conducted at the same timepoints as the blood sampling, the blood sampling should be conducted first before the dose of study medication is given.

## Appendix 2 - Haematology and Clinical Chemistry Parameters

### **Clinical Chemistry**

Sodium, potassium, chloride, total CO2, creatinine, glucose, blood urea nitrogen (BUN), albumin, total calcium, total magnesium, inorganic phosphorus, alkaline phosphatase, ALT/GPT, AST/GOT, total bilirubin, direct bilirubin, lactate dehydrogenase (LDH), total protein, total creatine kinase (CK), uric acid, glucose, insulin, Hb1Ac, total cholesterol, high density lipoprotein (HDL) cholesterol, low density lipoprotein (LDL) cholesterol, triglycerides, hsCRP, osteocalcin, CTX, plasma renin

### **Haematology**

#### Complete blood count (CBC):

Red blood cell count (RBC), red cell distribution width (RDW), haemoglobin (Hb), haematocrit (Hct), mean corpuscular volume (MCV), mean cell haemoglobin (MCH), mean cell haemoglobin concentration (MCHC) platelet count, white blood cell count (WBC), WBC differential count (% and absolute).

## Appendix 3 - Expected Adverse Events

The active ingredient of Chronocort® is hydrocortisone. The safety profile of hydrocortisone is well characterised in humans and there is extensive clinical experience with the use of hydrocortisone in subjects with CAH. The excipients used in the Chronocort® formulation are also well-characterised and approved for use in humans at the proposed levels. The risks of Chronocort® are, therefore, expected to be no greater than the risks of an equivalent dose of cortisol.

For US NIH clinical centre only (new text in bold): The active ingredient of Chronocort® is hydrocortisone. The safety profile of hydrocortisone is well characterized in humans and there is extensive clinical experience with the use of hydrocortisone in subjects with CAH. The excipients used in the Chronocort® formulation are also well-characterized and approved for use in humans at the proposed levels. The risks of Chronocort® are, therefore, expected to be no greater than the risks of an equivalent dose of cortisol. **However, until the safety, efficacy and tolerability of this formulation in the treatment of individuals with CAH has been proven, the risk is considered to be greater than minimal risk with the prospect of direct benefit in individual subjects.**

The Summary of Product Characteristics (SmPC) of hydrocortisone is used as the reference for expected AEs (<http://www.medicines.org.uk/emc/medicine/27652>). However, some of the data in the hydrocortisone SmPC clearly relates to anti-inflammatory immunosuppressive doses of glucocorticoid, which will not be used in this study of Chronocort®. Should such immunosuppressive events be observed they would be unexpected so are not included.

The following is reproduced from section 4.8 of the hydrocortisone SmPC:

The incidence of predictable undesirable effects, including hypothalamic-pituitary-adrenal suppression correlates with the relative potency of the drug, dosage, timing of administration and the duration of treatment. The following side effects may be associated with the long-term systemic use of corticosteroids:

*Gastrointestinal:*

Dyspepsia, peptic ulceration with perforation and haemorrhage, abnormal distension, oesophageal ulceration, candidiasis, acute pancreatitis.

*Musculoskeletal:*

Proximal myopathy, osteoporosis, vertebral and long bone fractures, avascular osteonecrosis, tendon rupture.

*Fluid and electrolyte disturbance:*

Sodium and water retention, hypertension, potassium loss, hypokalaemic alkalosis.

*Dermatological:*

Impaired healing, skin atrophy, bruising, striae, acne, telangiectasia.

*Endocrine/metabolic:*

Suppression of the hypothalamo-pituitary-adrenal axis, growth suppression in infancy, childhood and adolescence, menstrual irregularity and amenorrhoea. Cushingoid facies, hirsutism, weight gain, impaired carbohydrate tolerance with increased requirement for antidiabetic therapy, negative protein and calcium balance, and increased appetite.

*Neuropsychiatric:*

Euphoria, psychological dependence, depression, insomnia and aggravation of schizophrenia. Increased intracranial pressure with papilloedema in children (pseudotumour cerebri), usually after treatment withdrawal. Aggravation of epilepsy.

*Ophthalmic:*

Increased intra-ocular pressure, glaucoma, papilloedema, posterior subcapsular cataracts, corneal or scleral thinning, exacerbation of ophthalmic viral or fungal diseases.

*Cardiovascular:*

Myocardial rupture following recent myocardial infarction.

*General:*

Hypersensitivity, including anaphylaxis has been reported. Nausea, malaise, leucocytosis, thromboembolism.

*Withdrawal symptoms:*

Too rapid a reduction of corticosteroid dosage following prolonged treatment can lead to acute renal insufficiency, hypotension and death. A withdrawal syndrome may also occur including fever, myalgia, arthralgia, rhinitis, conjunctivitis, painful itchy skin modules and weight loss.

A wide range of psychiatric reactions including affective disorders (such as irritable, euphoric, depressed and labile mood, and suicidal thoughts), psychotic reactions (including mania, delusions, hallucinations, and aggravation of schizophrenia), behavioural disturbances, irritability, anxiety, sleep disturbances, and cognitive dysfunction including confusion and amnesia have been reported. Reactions are common and may occur in both adults and children. In adults, the frequency of severe reactions has been estimated to be 5-6%. Psychological effects have been reported on withdrawal of corticosteroids; the frequency is unknown.

In addition, 3 out of 16 subjects in a phase 2 study of Chronocort® had symptoms of carpal tunnel syndrome (median nerve compression), which may be related to fluid retention secondary to Chronocort® treatment.

## Appendix 4 - Sick Day Rules

Each site should follow their own sick day rules, or if these are not available then the following rules should be used:

### ADRENAL INSUFFICIENCY

Your body does not make adequate cortisol or aldosterone. Cortisol is a hormone which has many purposes in the body including maintaining blood pressure. Normally cortisol is secreted in the body in small amounts every day by the adrenal glands. In addition to the usual production of cortisol, the body normally has the ability to increase cortisol production in response to various stressors such as infection or trauma. Aldosterone is a hormone which is important in regulating salt and water balance. Sufficient aldosterone is necessary to prevent dehydration. These two hormones are being replaced in your body by medications.

Extra hydrocortisone must be given during times of **extreme physical stress** such as illness with fever and significant trauma.

For illnesses which result in:

Fever greater than or equal to 100°F (37.7°C)/ minor illnesses: take 10mg **Hydrocortisone** three times a day in addition to the usual daily dose of Chronocort®.

Fever greater than or equal to 101°F (38.3°C)/ more severe illness: take 20mg **Hydrocortisone** three times a day in addition to the usual daily dose of Chronocort®.

Vomiting: If you vomit, wait one half-hour and then take 20mg of hydrocortisone for sick day rules from your packet provided. If you vomit the Chronocort® dose do not take another dose of Chronocort® until the next dose is due. Call the study team to let us know you are sick. If you are vomiting and cannot keep the medication down (vomit less than 1 hour after the dose), you need to administer injectable hydrocortisone. **Do not delay giving injectable hydrocortisone.** Drink **SMALL** amounts of clear liquids frequently, as tolerated. Call your doctor or go to an emergency room if your symptoms worsen or you do not improve within one hour.

Watch for signs of acute cortisol deficiency: headache, nausea, abdominal pain, dehydration, confusion, weakness, fatigue.

An injectable form of hydrocortisone must be kept in an easily accessible location for emergencies (i.e. purse, briefcase, desk at work). It may be kept for several years in the unmixed form at room temperature. It should not be exposed to extreme hot or cold (i.e. do not store in the glove compartment of a car). Check the expiration date routinely and obtain a prescription refill when needed. Also make sure you have the needle necessary to inject the medication.

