The risks associated with this study include those associated with blood sampling and general involvement with clinical trials. The investigators in this trial are all highly experienced both in clinical trials and in the management of patients with CAH, and these risks are then negligible. In addition, to minimise the risk of anaemia associated with the withdrawal of multiple blood samples for laboratory testing (as seen in a previous study), the planned total blood volume to be withdrawn during this study has been limited to a maximum of 427mL. The other risks then relate to the potential under- or over-treatment of subjects with glucocorticoids as seen in day-to-day clinical practice. These risks apply to both conventional treatment and Chronocort®. The patients will be informed of the potential for under-treatment (as occurs when there is an intercurrent illness) and are taught to manage this with supplemental steroids (emergency pack for sick day rules) and to seek medical assistance. It is also possible that the new formulation of Chronocort® might fail to release properly in the gut with resultant low levels of cortisol. If this were to occur once, the associated risk would be low, as a subsequent dose would be given either 8 or 16 hours later with little consequence. It would be hazardous if this occurred repeatedly. However, the formulation technology used is commonly used for other pharmaceuticals, and the studies so far in healthy subjects and subjects with CAH do not suggest that this happens. If this were to occur, then sick day rules would come into force as the subjects would become unwell. Such episodes would also be identified as AEs, which would come to the notice of the Data Safety Management Board (DSMB). The DSMB will meet on a regular basis during the study to review the safety data and will operate in accordance with a predefined charter.

Over-treatment with hydrocortisone is unfortunately common in this condition as physicians try to control the cortisol levels. Regular assessment of the subjects (both biochemically and clinically) in the study will identify over-treatment and correct it through a reduction in dose.

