### ***10.5 Other Study Medications (Non-Investigational Medicinal Products)***

Stress doses to be used when the "sick day rules" are implemented will be supplied by the study site as part of a safety pack, which will typically include (according to local practice):

- A one-week supply of 20 mg oral hydrocortisone (in 10mg tablets to allow dosage of up to 20mg three times daily)
- 2 vials of hydrocortisone for injection plus syringes and needles
- The site's standard information guidance regarding "sick day rules" (routinely given to any subject receiving hydrocortisone replacement therapy)

Diurnal will also provide appropriate labels for the safety pack that the pharmacy can use to label the drugs dispensed to subjects (See Appendix 9). The subject number will be written on the safety pack by the pharmacist.

Subjects will continue to take Chronocort® twice daily or standard glucocorticoid replacement therapy at the usual dosing regimen when taking stress doses. Any additional doses of hydrocortisone needed should only be taken from the safety pack and should not be taken from the study medication pack.

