### **11.3 Sick Day Rules**

All subjects will be educated regarding "sick day rules". "Sick day rules," a written guideline regarding what to do during any illness, will be given to the subjects (as is done for all CAH subjects). Where sites have a standard set of "sick day rules" these will be supplied to subjects at that site routinely along with an emergency pack of medication (see Appendix 4 for an example of sick day rules that can be used for this study if a site chooses to do so). Use of sick day rules will be recorded in eCRF, including both duration, dose of steroid and use of injection. Sick day rules from each site will be collected prior to the beginning of recruitment and placed on file by the Sponsor.

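### Both fever instructions in the fallback sick-day handout (Appendix 4) name only Chronocort as the maintenance drug, which does not fit comparator subjects or match Section 10.5

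*Protocol*

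**What the plan says.** Protocol Section 11.3 requires all subjects to be educated about sick day rules and to hold them in writing: "a written guideline regarding what to do during any illness, will be given to the subjects". Sites with their own rules use those. Appendix 4 covers the rest. Section 11.3 presents it as optional ("see Appendix 4 for an example of sick day rules that can be used for this study if a site chooses to do so"), while the appendix itself is more directive: "Each site should follow their own sick day rules, or if these are not available then the following rules should be used". Neither place limits it to one arm, and the documents contain no comparator version.

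The handout has two fever tiers. From 37.7°C, or for minor illness, the subject takes 10 mg hydrocortisone; from 38.3°C, or for more severe illness, 20 mg. Both lines end with the same direction: "three times a day in addition to the usual daily dose of Chronocort".

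Section 10.5 gives the general rule for stress dosing in both arms: "Subjects will continue to take Chronocort® twice daily or standard glucocorticoid replacement therapy at the usual dosing regimen when taking stress doses". Section 10.2 confirms that comparator subjects remain on the standard glucocorticoid they were already receiving.

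The Benefit/Risk Assessment in Section 5 discusses under- and over-treatment, gives intercurrent illness as an occasion for under-treatment, and states: "These risks apply to both conventional treatment and Chronocort".

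**The concern.** A comparator subject with a fever, at a site using Appendix 4, reads an instruction to add hydrocortisone to a drug they do not take. Nothing in the two lines says that their own prednisolone, dexamethasone or hydrocortisone carries on. The protocol's rule has two halves, one per arm, and the handout keeps only the Chronocort half.

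The wording is least clear for comparator subjects on hydrocortisone alone, which is one of the three randomisation strata. They have no Chronocort to add to, and the stress drug is the same substance as their maintenance drug. They could read the tier as a total daily dose rather than a supplement. That is a possible misreading; the documents do not show that it happened.

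What is at stake is the clarity of a home-use safety instruction for people with adrenal insufficiency. Supplemental steroid in illness is one of the measures on which Section 5 relies to contain the risk of under-treatment, and Section 5 says that risk is shared by both arms.

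**Working it through.** The plan states no figure on this point, so the check is mainly a comparison of text, with simple arithmetic for scale.

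**Texts side by side**

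| Source | Reader | Maintenance drug named during stress dosing |
|---|---|---|
| Section 10.5 | Site staff | Chronocort or standard therapy |
| Appendix 4, lower fever tier | Subject | Chronocort only |
| Appendix 4, higher fever tier | Subject | Chronocort only |

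So 2 of 2 fever tiers name Chronocort alone. Standard therapy, prednisone, prednisolone and dexamethasone appear in 0 of 2.

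**Who can receive the handout.** Section 11.3 covers all subjects, and Appendix 4 is a single text for both. A comparator subject at a site using the fallback therefore receives the Chronocort wording.

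**Stress dose in each tier** (Appendix 4)
- Lower: 3 × 10 mg = 30 mg/day.
- Higher: 3 × 20 mg = 60 mg/day.

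Both are stated in full and are the same for either arm. The supplement is not in error; only the drug to which it is added is.

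**Scale of the possible misreading.** Section 5 gives a phase II mean of 28 mg hydrocortisone equivalent on standard therapy. Taking that as a typical maintenance dose, which is an assumption for illustration, Section 10.5 intends 28 + 30 = 58 mg/day in the lower tier. Read as a total, the same line gives 30 mg/day, close to an ordinary day's dose.

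**Number of subjects.** The protocol randomises 120. The allocation ratio is not stated; at 1:1 the comparator arm has 120 × 0.5 = 60. The number of sites using Appendix 4 is not given and could be none. The range is 0 to about 60 holders of the handout, and fewer with a febrile illness.

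**The vomiting paragraph.** Its rescue steps suit both arms: "If you vomit, wait one half-hour and then take 20mg of hydrocortisone for sick day rules from your packet provided", and "If you are vomiting and cannot keep the medication down (vomit less than 1 hour after the dose), you need to administer injectable hydrocortisone". Its advice on a vomited maintenance dose mentions Chronocort only, so it says nothing about retaking a vomited dose of standard therapy. That is a small gap and is not part of this point.

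**The case against.** The strongest reply is that the omission has little practical weight. Section 10.5 already states the correct rule. The stress dose is complete, and nothing tells anyone to stop standard therapy. The handout speaks of extra hydrocortisone, taken on top of a usual dose. Its readers are adults with classic CAH diagnosed in childhood, at least six months on stable treatment, and taught how to manage illness. The sites are described as experienced, their own rules take priority, and the upper bound of 60 requires every site to use the fallback. On this view *incomplete* describes the fever lines better than *wrong*.

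Most of this stands. It limits the exposure and makes harm unlikely, and it is why no shortfall is claimed. It does not remove the defect. Section 10.5 is protocol text for staff, whereas the handout is what the subject reads at home. The drug named is inapplicable to comparator subjects, and the correct instruction is missing from the page.

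A second reply is that correcting the fever lines while leaving the vomiting line as it is gives a half-corrected handout. The two differ. For the fever lines, Section 10.5 supplies the right rule, so the change needs no clinical judgement. The Chronocort advice on retaking a vomited dose may not carry over to other glucocorticoids, and the protocol gives no rule from which to take the wording.

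**Conclusion.** The point holds. Both fever tiers of Appendix 4 name only Chronocort as the maintenance drug, the handout has no comparator version, and it does not match the two-arm rule in Section 10.5.

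The size is small: two lines, at sites that use the fallback, for between 0 and about 60 comparator subjects. The upper bound assumes 1:1 allocation and use of Appendix 4 at every site; the lower bound is a real possibility. The documents do not show that any comparator subject received the text or took too little steroid, and no effect on the efficacy results follows. It is a patient-safety wording correction that should be made because the error in the text is certain and the remedy is already in the protocol.

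**What to change.** In both fever lines of Appendix 4, replace the word Chronocort® with: *your usual study glucocorticoid (Chronocort® or your standard therapy)*. This applies the sponsor's own rule from Section 10.5. The stress doses, the fever thresholds and the vomiting steps stay as they are.

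The cost is one phrase in two lines, plus re-issue of the handout and notification of the ethics committees at the sites that use it. Section 11.3 has the sponsor collect each site's sick day rules before recruitment, so those sites, if there are any, can be identified from the sponsor's file. No design or analysis figure changes.

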**Your dose of hydrocortisone for injection is 100 mg - 2mL by intramuscular injection to the thigh.**

Other points to remember:

- When you are sick, drink sugar and salt containing liquids (e.g. non-diet soda, Gatorade, Lucozade, soup).
- If you need to have surgery, extensive dental work, or you have been in an accident, extra doses of hydrocortisone will be needed, usually by intramuscular injection or intravenous administration. Notify any physician or dentist that you have ADRENAL INSUFFICIENCY, so proper amounts of hydrocortisone can be given prior to a procedure.
- It is essential that you wear a medical identification bracelet or necklace to alert people in times of emergency that you have adrenal insufficiency and are taking medication. It is also a good idea to have a wallet card or something on your driver's licence identifying you as having ADRENAL INSUFFICIENCY.
- Call your doctor for:  
Fever for more than three days  
Changes in behaviour, such as acting confused
- If you are living with someone, let them know to seek medical help on your behalf if you are unresponsive or difficult to arouse.

Ensure that you have a list of important phone numbers:

Nurse:

Doctor:

Pharmacy:

